### 2.6.2 Statistical and Analytical Plans

#### *Primary Endpoint Analysis*

The co-primary endpoints are the change in mean of second and third systolic and diastolic BP measurements taken at Visit 1 (pre-intervention) and at Visit 3 (at the end of week 4 of the intervention). Initially, sample mean and standard deviation will be reported at baseline and follow up. Moreover, their mean difference and standard deviation will be reported. Secondly, the main analysis will be conducted using a Gaussian linear mixed effects (LME) model with a first-order autoregressive correlation structure (AR(1)). The repeated measures are the BP results at Visit 1 and Visit 3. An interaction parameter between Visit and Arm of study will be the determinant of a significant difference in BP change between the two arms. The model will be adjusted for the following prognostic factors: age, eGFR and baseline serum nitrate/nitrite levels. The sensitivity analysis will only be adjusted for age and eGFR. Should any variables differ significantly between the two arms, they too will be adjusted for to eliminate the possibility of a confounding effect. No subgroup analyses will be undertaken. All data analysis will be completed in R version 3.6.2 (R Core Team). All (potential) confounding variables will be summarised using t-tests or rank sum tests for continuous variables and chi-squared tests or Fisher's exact tests for categorical variables. Means (standard deviations) and counts (column percentages) as well as relevant p-values will be reported. Hypotheses will be conducted with a two-sided alternative and p-values less than 0.05 will be considered statistically significant.

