#### **2.8.2 Randomisation**

Eligible participants will be randomised 1:1 at Visit 1 to receive either dietary nitrate or placebo using a simple randomisation program created by the study biostatistician, which uses a random number generator (version 3.6.2, R Core Team). This program creates a list that allocates treatment or placebo (1:1) to 60 unique study IDs. No stratification factors will be used. Participants will not consume the intervention until instructed to by trial staff at Visit 2.

If a participant is deemed ineligible between Visit 1 and 2, they will be asked to return the sealed beetroot juice given to them to the trial staff. The AI who is responsible for blinding will reallocate the BRJ as per the randomised number list created by the statistician.

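### The rule that adds significantly imbalanced variables to the primary model selects on chance, has no effect as a main effect with complete data, and cannot rule out confounding as it claims

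*Combined protocol and SAP*

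**What the plan says.** Section 2.6.2 (Primary Endpoint Analysis), repeated in the Summary table, sets out the model for the co-primary systolic and diastolic endpoints.

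- **Data:** "The repeated measures are the BP results at Visit 1 and Visit 3", fitted by a linear mixed model with AR(1) correlation.
- **Test parameter:** "An interaction parameter between Visit and Arm of study will be the determinant of a significant difference in BP change between the two arms".
- **Named covariates:** "The model will be adjusted for the following prognostic factors: age, eGFR and baseline serum nitrate/nitrite levels".
- **Added covariates:** "Should any variables differ significantly between the two arms, they too will be adjusted for to eliminate the possibility of a confounding effect".
- **How the arms are compared** (the last two tests being for categorical data): "All (potential) confounding variables will be summarised using t-tests or rank sum tests for continuous variables and chi-squared tests or Fisher's exact tests for categorical".
- **Threshold:** "Hypotheses will be conducted with a two-sided alternative and p-values less than 0.05 will be considered statistically significant". No separate level is given for the arm comparison.

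On allocation, section 2.8.2 says "This program creates a list that allocates treatment or placebo (1:1) to 60 unique study IDs" and "No stratification factors will be used".

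Nowhere do the documents list the variables to be compared, or say whether an added variable enters as a main effect or with a Visit interaction.

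**The concern.** Under random allocation, a test of a baseline difference tests a null hypothesis that is true by design. A small p-value marks an unlucky draw. It does not show that the variable is related to blood pressure. Choosing covariates this way can bring in irrelevant variables and leave out prognostic ones whose imbalance fell short of significance.

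The way the treatment effect is defined adds a second problem. It is a difference in change between two visits, and a time-constant main effect cancels out of a change. The result therefore depends on a form of entry that the plan does not state. In one form the rule does nothing. In another, the primary estimate depends on which arm comparisons happened to fall below 0.05. Two analysts following the same text could report different primary results, and readers would be told that confounding had been ruled out when it had not.

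**Working it through.** **Inputs from the documents.** Section 2.6.1 gives a 7.7 mmHg systolic effect, SDs of 10 and 11, alpha 0.05, power 0.80, 28 per arm, raised to 30 for drop-out. I use 10.5 as a middle SD. Treating it also as the SD of the change is my assumption. The drop-out allowance is 2 per arm, or 4 of 60 (6.7%).

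**The plan's own figure.** For 7.7 mmHg, two-sided 0.05 and power 0.80, the t-based sample size at SD 10 is 27.5, so 28 per arm. This reproduces the plan. It does not depend on the covariate rule; I use 7.7 mmHg only as a yardstick.

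**1. Main effect, complete data.** Write participant i's values as y1 and y3, with covariate x entering as c·x at both visits. Then

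y3 − y1 = (Visit effect) + (Visit by Arm)·arm + error,

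because c·x cancels. With two visits, AR(1) with equal variances is simply one correlation. The sum and the difference of the two values are then uncorrelated, and the interaction is estimated from the differences alone. In four simulated trials fitted by REML, with a built-in imbalance and a covariate that truly predicted the change, estimate and standard error agreed to five decimals with and without the covariate (for example −6.83842, SE 2.54641, both times). The same algebra applies to age, eGFR and baseline nitrate/nitrite if they enter as main effects.

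**2. Main effect, 4 of 60 Visit 3 values missing.** Participants with one visit add some between-person information, so the shift is no longer exactly zero. With a flagged covariate and assumed visit correlations of about 0.4 to 0.8, it is typically 0.05 to 0.14 mmHg, or 0.05/7.7 = 0.6% to 0.14/7.7 = 1.8% of the target. Shifts near 0.5 mmHg occur only as extremes.

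**3. Entry by Visit.** The shift is approximately

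imbalance (in SD) × correlation of x with the change × SD of the change.

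The smallest imbalance that is flagged at 30 per arm is t(0.975, 58 df) × √(2/30) = 2.0017 × 0.2582 = 0.52 SD. At that imbalance:

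| Assumed correlation with the change | Shift (mmHg) |
|---|---|
| 0.1 | 0.52 × 0.1 × 10.5 = 0.5 |
| 0.2 | 0.52 × 0.2 × 10.5 = 1.1 |

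Simulation likewise gives roughly 0.5 to 1 mmHg on average. The four REML examples, built with a strong covariate (4 mmHg per SD on the change, expected imbalance 0.7 SD), moved by 0.7 to 2.6 mmHg.

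**4. Chance that something is flagged.** For k independent variables it is 1 − 0.95^k:

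| k (assumed) | Chance of at least one flag |
|---|---|
| 5 | 1 − 0.774 = 23% |
| 10 | 1 − 0.599 = 40% |
| 20 | 1 − 0.358 = 64% |

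**5. What the rule leaves unadjusted.** Imbalances below 0.52 SD are not flagged. At that limit, the remaining shift at correlations of 0.3, 0.5 and 0.7 with the change is 1.6, 2.7 and 3.8 mmHg (0.517 × r × 10.5).

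**6. Error rate and power.** Simulation on change scores, 30 per arm, 5 or 10 independent, equally prognostic variables that jointly explain 25% or 50% of the change (all assumed):

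| | No covariates | Significance rule | Whole set fixed in advance |
|---|---|---|---|
| Type I error | about 5% | 3.5–4.5% | about 5% |
| Power at 7.7/10.5 SD | 79–80% | 79–81% | 83–96% |

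When a variable was flagged, the significance verdict differed from the unadjusted one in 12–21% of trials under the assumed effect and 5–10% under the null.

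**The case against.** The strongest defence is that the rule hardly matters. Adjustment, read in the ordinary way, means main effects, and then the interaction does not move. Section 2.6.2 (Missing values) expects few missing primary values. The trigger is written down in advance, and the outcome, model, correlation structure, test parameter, three covariates and threshold are all fixed. This stands as a statement about size: under the likeliest reading, the numerical effect is nil or negligible. It does not rescue the rule, because a rule that changes nothing cannot remove confounding either.

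A reader might go further than the documents allow in four ways.

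- **That false positives are inflated.** The simulation shows the opposite, a slightly conservative test.
- **That the planned model would shift by 1 to 2 mmHg.** Average shifts of that order need covariate-by-Visit terms with a strongly prognostic variable, or a model for Visit 3 adjusted for baseline. The plan specifies neither.
- **That the primary analysis as a whole is not pre-specified.** Only the list of added variables and their form of entry are open.
- **That variables measured after randomisation would be adjusted for.** The sentence does not say baseline, so the wording does not exclude it, but nothing in the plan states such an intention.

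It is also fair to say that a flagged variable entered by Visit does have its own imbalance removed. The complaint is about the much wider assurance the plan gives.

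**Conclusion.** The concern holds as a faulty covariate rule on the co-primary endpoints, and should be corrected before unblinding. It does not threaten the validity of the trial. That a main effect leaves Visit by Arm unchanged with complete data is algebra and needs no assumption beyond the stated model. The shifts of 0.05 to 0.14 mmHg with 4 of 60 missing, and of roughly 0.5 to 1 mmHg on average (more in some trials) with entry by Visit, rest on assumed correlations. The flag probabilities rest on an assumed number of independent variables. Whichever form of entry is used, non-significant imbalances up to about 0.52 SD stay unadjusted, so the stated aim is not met. The cost is an undetermined part of the primary model, a false assurance and forgone precision.

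**What to change.** Delete the sentence, here and in the Summary, and do not use arm-comparison tests to choose covariates. Fix the set in advance: age, eGFR and baseline nitrate/nitrite as already planned, plus the baseline value of the blood pressure outcome being analysed. State the form in which they act on Visit 3 blood pressure: either a baseline-adjusted (ANCOVA) model, or an equivalent model with baseline means constrained equal across arms and covariate-by-Visit terms. This also makes the three named covariates do some work. Label any further adjustment as a sensitivity analysis.

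The cost is that the form of the primary model is rewritten in the SAP, which is more than deleting a line. No extra data or procedures are needed, since baseline blood pressure is already measured at Visit 1, and the sample size need not change. Dropping p-values from the baseline table is an optional reporting choice.

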#### *Secondary Endpoint Analysis*

The secondary endpoint of home BP readings is a set of (at most) 28 daily systolic and diastolic BP measurements averaged from daily home readings. Again, a Gaussian LME model with an AR(1) correlation structure will be utilised. The repeated measures are the BP results at each available home reading. An interaction parameter between Day and Arm of study will be the determinant of a significant difference in the BP change between the two arms. The model will be adjusted for the prognostic variables of age, eGFR and

baseline nitrate/nitrite levels as described above. The secondary endpoints of change in NO metabolites, serum ADMA and albumin to creatinine ratio will have their differences summarised with sample means, standard deviations, sample mean differences, and sample standard deviations of differences. They too will undergo assessment with a Gaussian LME model as above.

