| Study Design          | This is a randomised, double blind placebo-controlled trial. Participants with treated hypertension (defined as being on at least one anti-hypertensive medication; n=60) will be included in the study. The total duration of the study is 5 weeks. There will be a 7 day run-in period where participants will be asked to record BP daily to determine adherence and baseline blood pressures. Participants will then be randomised (1:1) to receive an oral daily dose of either BRJ (400mg nitrate) or nitrate-depleted BRJ for 28 days. Blood pressure will be measured in clinical and at home using a standard and validated automated oscillometric blood pressure (AOBP) device provided to all participants. Blood, urine and saliva samples will be collected before and after the intervention. |
| Primary Endpoint      | Reduction in mean automated clinic systolic and diastolic blood pressure relative to baseline  |
| Secondary Endpoint    | 
 
Change from baseline in the mean home systolic and diastolic blood pressure
 
Change in urinary albumin to creatinine ratio
 
Change from baseline in plasma and urine nitrate, NO metabolites, and ADMA levels
 
  |
| Planned Sample Size   | A total of 60 treated hypertensive participants (1:1; male and female; aged 18-70 years old) with ADPKD (as per the inclusion/exclusion criteria) will be randomised.  |
| Inclusion Criteria    | 
 
Diagnosis of ADPKD
 
Age over 18 years old
 
eGFR > 30 mL/min/1.73m^2
 
Treatment with at least one anti-hypertensive
 
  |
| Exclusion Criteria    | 
 
Inability to provide Informed Consent
 
Labile, unstable uncontrolled hypertension and/or changes in blood pressure treatment in the last 28 days prior to the screening visit that in the opinion of the investigators would confound interpretation of the primary endpoint
 
Non-compliance with daily BP measurements during the screening period
 
  |

|                                       |   |
|---------------------------------------|---|

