### 2.2.2 Secondary Endpoints

The secondary outcomes assessing treatment efficacy in this study will be the change from baseline in the following:

- (a) mean daily home systolic and diastolic systolic and diastolic blood pressures
- (b) change in urinary albumin to creatinine ratio
- (c) levels of NO metabolites (nitrate and nitrite) in plasma and urine; and
- (d) plasma ADMA levels after dietary nitrate supplementation using BRJ.

To assess safety of chronic nitrate supplementation, the frequency and type of adverse events will be evaluated

To assess adherence to the study procedures, the following will be assessed:

- (a) Number/percent of completed/missed measurement of blood pressure as represented by response to automated text messages or completion of patient diary
- (b) Of measurements captured, number/percent of those who consumed BRJ and took measurements in morning period (6am-9am).

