## 2.4 Study Design

[figure not shown]
The total duration of the study is 35 days. Patients will be screened at Visit 1 and eligible patients will be provided with a blood pressure monitor (oscillometric BP device: UA-651, A&D Medical, Tokyo, Japan) to commence baseline home blood pressure monitoring for a 7 day run-in. Their compliance to daily blood pressure readings will be assessed via automated text message each morning (to which participants will reply with their readings), or with a phone call by study staff on Day 2 and 5 if they opt-out of text messages, and at Visit 2. Replying via text message will be encouraged as the preferred option as it will allow for real-time monitoring and data recording and allow patients to easily contact the study team if they have any issues. Participants will be randomly allocated nitrate-rich BRJ (400mg nitrate) or nitrate depleted BRJ (placebo) in a sealed bag and asked not to open it until instructed to do so after Visit 2.

At Visit 2 (conducted via phone), participants' home blood pressure records will be reviewed for compliance. Participants who have recorded  $<80\%$  of the daily blood pressure readings will be deemed non-compliant and excluded from the trial. Additional exclusion criteria assessed at Visit 2 includes eGFR, fasting lipid and glucose levels, use of antiseptic mouthwash (from V1 to V2 and willingness to comply for remainder of study). Any excluded participants will be asked to return all study equipment and the sealed bag of BRJ. Participants who meet all criteria will be asked to commence the intervention that they were allocated the following morning.

The intervention is BRJ commercially packaged BRJ in 70ml bottles. Participants will be instructed to drink one bottle per day (70ml) and measure their blood pressure at the same time every day. Participants will be asked to send their blood pressures via text or record it in their diary. A daily reminder text message will be sent, unless participants opt-out of this option.

After 28 days, participants will return for Visit 3 for post-treatment assessment and sample collection.

Blood and urine samples will be collected at Visit 1 and 3 for measurement of NO metabolites, ADMA levels and urinary albumin to creatinine ratio. A saliva sample will be collected at Visit 1 and 3 for future genomic analysis of oral bacteria.

**Figure 2.** Study design and participant timeline

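### The deciding test for home BP (Day × Arm over at most 28 daily values) does not estimate the stated endpoint, change from the run-in baseline in mean home BP

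*Combined protocol and SAP*

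**What the plan says.** **Endpoint.** The Summary lists as a secondary endpoint "Change from baseline in the mean home systolic and diastolic blood pressure". Section 2.2.2 agrees: "The secondary outcomes assessing treatment efficacy in this study will be the change from baseline in the following", with home BP first on the list.

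**Baseline.** The Summary (Study Design) says: "There will be a 7 day run-in period where participants will be asked to record BP daily to determine adherence and baseline blood pressures". Section 2.4 has participants given a monitor "to commence baseline home blood pressure monitoring for a 7 day run-in".

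**Analysis.** Section 2.6.2, Secondary Endpoint Analysis, repeated in the Summary, says: "The secondary endpoint of home BP readings is a set of (at most) 28 daily systolic and diastolic BP measurements". The model is a Gaussian mixed model with AR(1) correlation. On the data it says: "The repeated measures are the BP results at each available home reading". The covariates are age, eGFR and baseline nitrate/nitrite. The decision rule is: "An interaction parameter between Day and Arm of study will be the determinant of a significant difference in the BP change". The plan does not say whether Day is linear or categorical.

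**The concern.** The limit of 28 values equals the number of intervention days, and no run-in home BP appears in the model as a repeated measure or a named covariate. A Day × Arm term fitted to on-treatment days alone measures whether the gap between arms changes from one treatment day to another. It does not measure how far each arm has moved from its run-in level.

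The co-primary analysis uses parallel wording without this problem. There the repeated measures are Visit 1 and Visit 3, so Visit × Arm is a contrast in change from baseline. Replacing Visit by Day over the treatment period removes the baseline time point.

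At stake is the conclusion on one secondary endpoint. It would depend on when an effect begins as well as on how large it is. A late divergence would be a genuine difference between randomised arms, but it is not the stated quantity.

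**Working it through.** **The plan's own figure.** There is no sample size or power statement for home BP. The only one, 28 per arm in section 2.6.1, concerns clinic systolic BP. It reproduces with SD 10 (two-sided 5%, power 0.80, difference 7.7 mmHg): 2 × (1.96 + 0.84)² × 10² / 7.7² ≈ 26.5, so 27 by the normal formula and 28 by the t-based one. It has no bearing here.

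**Which quantity is tested.** Let δ(t) be the arm difference on treatment day t. The endpoint concerns the average of δ(t) relative to the run-in, where the expected difference is zero. Day × Arm over days 1–28 tests whether δ(t) varies with t. If δ(t) is constant, the interaction is zero whatever the size of δ, with Day linear or categorical, and the test rejects only at its 5% level. This needs no variance assumption.

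**Power: inputs.**
- From the documents: 30 per arm; two-sided 5%; treatment days 1–28; run-in home BP on days −6 to −1 (the six days marked in Appendix A); effect 7.7 mmHg (the clinic figure in section 2.6.1), repeated at 7.3 mmHg (the home systolic figure cited in section 2.7.2).
- Assumed: complete data and 15 covariance settings. Twelve have a random-intercept SD of 8 or 9, within-person SD of 6 or 8, and AR(1) correlation of 0.2, 0.5 or 0.7. Three are pure AR(1) with SD 10 and correlation 0.5, 0.65 or 0.8.
- Assumed: no effect on the Day 1 reading unless stated, because Appendix C has BP taken straight after the dose.

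**Formulas.** Let V be the within-person covariance matrix.
- Slope: X has columns 1 and t; SE² = (2/30) × the slope element of (X′V⁻¹X)⁻¹.
- 28-day mean adjusted for the run-in mean: SE² = (2/30) × [var(treatment mean) − cov(treatment mean, run-in mean)² / var(run-in mean)].
- Power ≈ Φ(|effect|/SE − 1.96).

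**One setting in full** (SDs 9 and 8, correlation 0.5). The slope SE is 0.0755 mmHg per day and the adjusted-mean SE is 1.29 mmHg.
- Half effect from Day 2, rising linearly to full on Day 28. Slope difference 0.196: 0.196/0.0755 = 2.60, power 74%. Mean difference 7.7 × 0.75 × 27/28 = 5.57: 5.57/1.29 = 4.3, power 99%.
- Full effect from Day 15. Slope 0.389: ratio 5.2, power over 99%. Mean 3.85: ratio 2.98, power 85%.
- Full effect from Day 2. Slope 0.099: ratio 1.32, power 26%. Mean 7.43: ratio 5.7, power over 99%.

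**Range over the 15 settings, full effect 7.7 mmHg**

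| Time course | Linear Day × Arm | Run-in-adjusted 28-day mean |
|---|---|---|
| Half effect from Day 2, growing to full | 46–99% | 96–100% |
| Full effect from week 3 | 79–100% | 72–100% |
| Full effect from Day 2 (hypothetical) | 18–54% | over 99% |
| Full effect from the first reading (limiting case) | 5% | over 99% |

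For week-3 onset, Day × Arm leads by more than 1 point in 10 of the 15 settings and trails in 3. At 7.3 mmHg the first three rows become 42–98% against 94–100%, 75–100% against 68–100%, and 17–49% against over 99%.

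**The case against.** **The cited evidence favours a test of divergence.** Section 2.7.2 describes one four-week trial whose home effect both lasted and grew (one citation covers both statements), and another with a 7.3 mmHg home systolic effect in weeks 3 and 4. It also says that lowering was seen after at least 21 days. This stands. A reader might infer that the documents predict an early, flat effect and that the planned test therefore has almost no power. They do not: no cited home BP result shows that pattern, and the four-hour result in section 1.1.4 is not described as home BP. The 18–54% row is hypothetical. But suiting one time course does not make Day × Arm a test of the stated endpoint.

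**Run-in days might be included.** The wording about every available reading leaves room for this. With categorical Day and the run-in as reference level, Day × Arm would be a joint test of change from baseline: valid, but inefficient (about 38–100% for the growing effect, against 96–100%). The ceiling of 28 values counts against this reading. With linear Day and run-in days included, the term would still be a slope.

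**The imbalance rule might bring in the baseline.** For the primary analysis the plan says: "Should any variables differ significantly between the two arms, they too will be adjusted for". Even if that applied here and added run-in BP as a covariate, Day × Arm would still decide.

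**Mean may refer to averaging within a day.** Section 2.12.1 averages the second and third readings, and no section defines a 28-day mean. This stands in part: the averaging window proposed below is a choice that the plan has not made. The promise of change from baseline remains, and the model does not deliver it.

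**Conclusion.** The point holds as a mismatch between endpoint and deciding test, and should be fixed. On the most natural reading, the rule tests divergence between arms during treatment, with no home BP baseline in the model. That conclusion comes from the text and does not depend on the power figures.

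The size of the consequence does depend on assumptions, since all variances are assumed. For the time course closest to the cited persisting-and-growing study, the planned test has 46–99% power against 96–100%. For a late effect it usually does better than the 28-day mean. It would be wrong to conclude that Day × Arm is always the weaker test, or that the trial's main result is at risk: this is a secondary endpoint and the co-primary clinic BP analysis is sound on this point.

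**What to change.** 1. Define the home BP baseline as each participant's mean run-in home BP.
2. Make the deciding test the Arm contrast in on-treatment mean home BP over one pre-specified window (all 28 days, or weeks 3–4), adjusted for that baseline. A Period (run-in or intervention) × Arm term would be equivalent in aim.
3. State how Day is coded and whether run-in days are among the repeated measures. Keep Day × Arm as a supporting description of the time course.
4. Make the same change in the Summary, which repeats the analysis text.

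**Cost.** No new data are needed. The choice of window involves a trade-off. At 7.7 mmHg, the 28-day mean falls to about 72% at worst for week-3 onset. The weeks 3–4 mean keeps at least 97% in the first three rows of the table, but for an effect that is full at Day 2 and wanes to half by Day 28 it falls to about 79% at worst, against 96% for the 28-day mean.

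**Timing.** The stated timeline runs from May 2022 to April 2023, and section 2.8.1 keeps allocation blinded until data lock and analysis. The change should be dated and justified before unblinding, through the process in section 5.3 (Protocol amendments) if required. If allocation is already known, the new contrast should be labelled post hoc and reported beside the planned one.
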